10 CLINICAL MONITORING

10.1 Site Monitoring Plan

Site monitoring will be conducted to ensure that human subjects protections, study and laboratory procedures, study intervention administration, and data collection processes are of high quality and meet sponsor, ICH/GCP guidelines and applicable regulations, and that this study is conducted in accordance with the protocol, protocol-specific MOP and applicable sponsor standard operating procedures. DMID, the sponsoring agency, or its designee will conduct site-monitoring visits as detailed in the clinical monitoring plan.

Site visits will be made at standard intervals as defined by DMID and may be made more frequently as directed by DMID. Monitoring visits will include, but are not limited to, review of regulatory files, accountability records, eCRFs, informed consent forms, medical and laboratory reports, and protocol compliance. Site monitors will have reasonable access to the participating VTEU site, study personnel, and all study documentation according to the DMID-approved site monitoring plan. Study monitors will meet with the site principal investigators to discuss any problems and actions to be taken and document visit findings and discussions.

11 STATISTICAL CONSIDERATIONS

11.1 Introduction

This study will use a systems biology approach to get a better understanding of how human immune cells respond to influenza A/H7N9 vaccination on the molecular level and how the addition of AS03 adjuvant modulates this response.

Specifically, this study will assess and characterize changes in gene expression and protein abundance in immune cells obtained from healthy adults after each of two doses of a monovalent inactivated influenza A/H7N9 virus vaccine manufactured by Sanofi Pasteur administered intramuscularly approximately 28 days apart at 3.75 mcg of HA (A/Shanghai/2/2013) per 0.5 mL [adjuvanted] or 0.25 mL [unadjuvanted] dose given with or without AS03 adjuvant manufactured by GSK. We will also compare these responses to one dose of unadjuvanted monovalent inactivated influenza A/H3N2v virus vaccine manufactured by Sanofi Pasteur administered intramuscularly at 15 mcg of HA (A/Minnesota/11/2010) per 0.5 mL dose.

To elucidate the higher order organization of genes and proteins that differ between the three study arms, clusters with correlated response profiles, enriched functional modules and pathways as well as their placement within molecular networks will be determined. In addition, cytokine/chemokine concentrations well as serum anti-HA hemagglutination-inhibition (HAI) and neutralizing antibody concentrations will be measured. The goal is to correlate these measurements with responses on the molecular level to identify groups of genes and proteins that are associated with cytokine/chemokine production, seroconversion, or peak titer.

11.2 Study Hypotheses

This Phase II clinical study is not designed to test a specific hypothesis. Rather it is intended as an exploratory hypothesis-generating study to reveal new insights into how human immune cells respond to influenza A/H7N9 or A/H3N2 vaccination and how AS03 modulates responses to A/H7N9.

11.3 Study Outcome Measures

Refer to Section 3 for study outcome measures.

11.4 Sample Size Considerations

11.4.1 Study Design

This is a single center, randomized, partially-blinded, Phase II, small, targeted, prospective study in approximately 30 healthy male and non-pregnant female subjects aged 18 to 49 years old, inclusive, designed to evaluate and compare the immunogenicity between an intramuscular monovalent inactivated influenza A/H7N9 virus vaccine manufactured by Sanofi Pasteur given with and without AS03 adjuvant manufactured by GlaxoSmithKline, and an intramuscular unadjuvanted monovalent inactivated influenza A/H3N2v virus vaccine manufactured by Sanofi Pasteur.

This study will use a standard and systems biology approach to assess the human early gene and protein signatures expressed at baseline (approximately Days -7 and 1), and at approximately Days 2, 4, and 8 (A/H3N2v-vaccinated subjects only) after the first study vaccination in each treatment arm as well as at approximately Days 29, 30, 32, and 36 in A/H7N9-vaccinated subjects only. Cellular immunogenicity (systems biology studies) data will be integrated with serologic immunogenicity (HAI and Neut antibody assays) and reactogenicity data to develop a systems model of the human immune response to unadjuvanted monovalent inactivated influenza A/H3N2v virus vaccine and monovalent inactivated influenza A/H7N9 virus vaccine given with and without AS03 adjuvant.

This study will use venous blood samples and subject data collected from a total of thirty vaccinated subjects randomly divided into three equal treatment arms. The first treatment arm (n=10) will be vaccinated with one dose of 15 µg of A/H3N2v HA. The second treatment arm (n=10) will be vaccinated with two doses of 3.75 µg of A/H7N9 HA given with AS03 approximately 28 days apart. The third treatment arm (n=10) will be vaccinated with two doses of 3.75 µg of A/H7N9 HA given without AS03 adjuvant approximately 28 days apart. All study vaccinations will be administered intramuscularly.

Reactogenicity will be measured by the occurrence of solicited injection site and systemic reactions from the time of each study vaccination through 8 days after each study vaccination. Unsolicited non-serious adverse events (AEs) will be collected from the time of each study vaccination through approximately 28 days after each study vaccination. Serious adverse events (SAEs) and medically-attended adverse events (MAAEs) including new-onset chronic medical

conditions (NOCMCs) and potentially immune-mediated medical conditions (PIMMCs) will be collected from the time of the first study vaccination through approximately 1 month (A/H3N2v arm) and 12 months A/(H7N9 arms) after the last study vaccination.

Venous blood samples (approximately 90 mL) will be collected from subjects at approximately Days -7 and 1 (immediately prior to the first study vaccination), and at approximately Days 2, 4, and 8 (A/H3N2v-vaccinated subjects only), after the first study vaccination for systems biology studies (cytokine and chemokine levels, immune cell activation status, and whole transcriptome and proteome profiles of the major blood immune cells). Additionally, subjects in either treatment arm receiving A/H7N9 vaccine will have additional blood samples collected at approximately Days 29 (this will be collected immediately prior to the second study vaccination for subjects in either group receiving A/H7N9), 30, 32, and 36 after the first study vaccination for systems biology studies.

Serological assessment (hemagglutination inhibition (HAI) and neutralizing (Neut) antibody assays) will also be conducted on venous blood samples (approximately 10 mL) collected from subjects at Day 1 (immediately prior to the first study vaccination), and at approximately Days 29 (for A/H7N9-vaccinated subjects this will be collected immediately prior to the second study vaccination) and 57 (A/H7N9-vaccinated subjects only) after the first study vaccination.

We will quantify and characterize serum cytokine/chemokine levels, as well as transcriptomic and proteomic profiles from individual immune cell compartments, comparing this with standard serologic assessment to vaccine.

Urine samples (approximately 20 mL) will also be collected from subjects at approximately Days -7 1, 2, 4, 8 (A/H3N2v-vaccinated subjects only), 29, 30, 32, and 36 for future research. *Note: Days 29, 30, 32, and 36 will apply only to A/H7N9-vaccinated subjects.*

11.4.2 Study Population

The study population for this clinical study is approximately 30 healthy male and non-pregnant female subjects aged 18 to 49 years old, inclusive, who meet all eligibility criteria. The subjects will be recruited from the general population at the participating VTEU site that has substantial experience conducting influenza vaccine studies.

11.4.3 Sample Size

The sample size is not based on a formal hypothesis. Rather it is based on practical considerations with the goal of gathering enough information to learn more about immune system responses to the vaccine/adjuvant on the molecular level. DMID Protocol 10-0074,

entitled: “*A Randomized, Double-Blinded, Controlled, Phase I Study in Healthy Adults to Assess the Safety, Reactogenicity, and Immunogenicity of Intramuscular Subvirion Inactivated Monovalent Influenza A/H5N1 Virus Vaccine Administered With and Without AS03 Adjuvant: Standard & Systems Biology Analyses*”, showed that sample sizes in this range are sufficient to detect key differential signals and carry out systems biology analyses.

11.4.4 Planned Interim Analyses

Interim analyses would only be used to terminate this study in the event that unanticipated safety events deemed to be of sufficient concern require such action by the sponsor. These assessments will not be made on the basis of testing a formal statistical hypothesis; therefore, p-value adjustment will not be made to any analyses. A SMC will be convened by DMID to review study progress and participant, clinical, safety, and reactogenicity data.

11.4.5 Interim Safety Review

An interim safety review may include enrollment and demographic information, medical history, concomitant medications, physical assessments, and solicited and unsolicited AE/SAEs. Additional data may be requested by the SMC, and interim statistical reports may be generated as deemed necessary and appropriate by DMID. The SMC may receive data in aggregate and presented by treatment arm. The SMC may also be provided with expected and observed rates of the expected AEs in an unblinded fashion, and may request the treatment arm be unblinded for an individual subject if required for safety assessment. The SMC will review grouped and unblinded data in the closed session only. The SMC will meet and review this data at scheduled time points or ad hoc as needed during this study as defined in the SMC charter. As an outcome of each review/meeting, the SMC will make a recommendation as to the advisability of proceeding with study vaccinations (as applicable), and to continue, modify, or terminate this study.

Additionally, this study will be monitored to determine if any of the halting rules described in Section 9.5 are met.

11.4.6 Interim Immunogenicity Review

An interim immunogenicity review is not planned.

11.5 Final Analysis Plan

Prior to database lock, a Statistical Analysis Plan that will outline in detail the planned statistical analyses for this study will be developed and finalized. In the following section an abbreviated version is provided.

11.5.1 Systems Biology Analyses

11.5.1.1 Transcriptomics (RNA-seq)

RNA-Seq data will be pre-processed by removing adapters and low-quality reads and mapping sequences to the latest human reference genome using splice-aware alignment software such as HISAT2.. Gene expression quantification will be carried out by using *Subread* against a common gene model reference. Systematic differences between samples will be normalized using the TMM method as implemented in the *edgeR* R package. Post normalization, genes that are known ribosomal, transfer, and mitochondrial RNA genes or genes located on the X or Y chromosomes will be excluded to avoid gender-specific effects. Moderated log counts per million (LCPM) for the remaining genes will be determined using *edgeR*. LCPM will be used to identify lowly expressed genes, technical bias (e.g. batch effects or GC-content bias), and outlying samples. More specifically, Principal Component Analysis, non-metric multidimensional scaling, and correlation heatmaps based on LCPM will be carried out to identify potential global outliers and batch effects. Negative binomial models as implemented in *edgeR* will be used to determine differentially expressed genes for each endpoint and time point after removal of lowly expressed genes and outliers. If technical bias is detected and the effect is balanced across comparison groups, it will be accounted for by including a covariate as part of the negative binomial models. To compensate for testing multiple genes, p-values will be adjusted for by calculating false-discovery rates (FDR) based on the Benjamini-Hochberg procedure which controls the false positive rate among significantly differentially expressed genes. Genes with a FDR-value < 0.05 and a fold change of greater or equal to 1.5-fold (up or down regulation) will be deemed to be significantly differentially expressed (DE). Baseline responses (fold change in LCPM) of DE genes will be visualized using heatmaps. Unsupervised multiscale bootstrapping will be carried out to identify robust gene clusters with correlated responses (*pvclust* R package). Visualizations of fold change time trends for robust gene cluster will be provided. In addition, higher order organization of DE genes will be investigated using gene set enrichment analysis based on the latest MSigDB and KEGG databases accounting for gene length bias (*goseq* R package). Pathway maps color-coded by treatment effect will be provided for significantly enriched KEGG pathways. Experimentally determined protein-protein interaction networks including known Influenza A-host interactions centered around DE genes will be generated using data from the IntAct database and visualized using *Cytoscape*. Regularized canonical correlation

(*mixOmics* R package), linear and logistic regression models (*glmnet* R package) based on baseline fold change in LCPM will be carried out to determine gene responses that are correlated with cytokine/chemokine concentrations, peak titer, or seroconversion status, respectively.

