6.8. Multiple Comparisons/Multiplicity

No multiple testing adjustments will be carried out for the safety, immunogenicity, and cytokine/chemokine endpoints. For -omics endpoints, the false-discovery rates (FDR) based on the Benjamini-Hochberg procedure as implemented in the R *p.adjust* function will be used to control the false positive rate among significantly differentially expressed genes, proteins, and enriched pathways.

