9.2. Identification of Differentially Expressed Genes

Negative binomial generalized linear models as implemented in the edgeR software [10] will be applied to identify differentially expressed (DE) genes after exclusion of outlying samples and lowly expressed genes. TMM-adjusted total read counts per sample will be included in the models as an offset to account for systematic sample differences. If systematic technical bias is detected and the effect is balanced across study arms, it will be accounted for by including a covariate or factor as part of the negative binomial models.

For all study arms, DE gene analysis will be carried out for each post-first vaccination study day (Day 2, 4, 8 or 29) in relation to pre-first vaccination gene expression levels (Section 9.2.1). For Study Arms 2 and 3, DE gene analysis will be carried out for each post-second vaccination study day (Day 30, 32, and 36) in relation to pre-second vaccination (Day 29) gene expression levels (Section 9.2.2). In addition, differences in DE gene responses between Study Arms will be assessed for all possible pairwise study arm comparisons (Section 9.2.3).

To control for testing multiple genes, the false-discovery rate (FDR) based on the Benjamini-Hochberg procedure [12] as implemented in the *p.adjust* R function will be applied for each model. In all cases, genes with an absolute fold change (effect size) of ≥ 1.5 compared to pre-vaccination or between Study Arms and FDR-adjusted p-value < 0.05 will be considered significantly DE. Depending on observed magnitude of differential expression effects, the pre-specified fold change cut off of 1.5-fold may be revised. The number of DE genes will be tabulated by study arm and time point (Table 126 and Table 127). In addition, DE gene listings that include gene annotations, \log_2 fold change estimates, p-values, FDR-adjusted p-values, likelihood ratio statistic and average LCPMs will be provided for each post-vaccination day (Table 128).

Treatment effects in terms of overall fold changes and FDR-adjusted p-values will be summarized for all genes that passed the low expression cut off using MA plots and Volcano plots (Figure 9). Overlap in DE genes between post-vaccination days and Study Arms will be summarized using UpSet plots as outlined in Figure 10 both in terms of overall numbers and separately for up/down-regulated DE genes.

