9.2.1. Identification of DE Genes Compared to Pre-First Vaccination

For each post-first vaccination day and study arm, a negative binomial model will be fit to pre- and post-first vaccination read counts. Each model will include coefficients to estimate subject and pre- vs. post-first vaccination effects. The subject effects for estimating subject-specific pre-first vaccination levels will be added to account for paired samples from the same subject. Effects will be parameterized in the design matrix using dummy variables with one variable for each subject and an additional variable for the vaccination effect. For vaccination effects, the value will be set to 1 for post-first vaccination and 0 for pre-first vaccination observations. For each gene, the statistical significance of the post- vs. pre-vaccination effect will be evaluated using a likelihood ratio testing the following hypothesis on the \log_2 scale:

$$H_0: \mu_{\text{post-vaccination}} - \mu_{\text{pre-vaccination}} = 0, H_1: \mu_{\text{post-vaccination}} - \mu_{\text{pre-vaccination}} \neq 0$$

Genes with an absolute fold change (effect size) of ≥ 1.5 compared to pre-first vaccination and FDR-adjusted p-value < 0.05 will be considered to be significantly DE.

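### The false-discovery guarantee stated for differentially expressed genes does not carry over to the list that is also cut on an observed 1.5-fold change

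*Protocol*

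**What the plan says.** Primary endpoint 3 (Protocol 3, SAP 3.2) is the number of differentially expressed (DE) genes in the two A/H7N9 arms at each post-vaccination day. SAP Table 126 gives the counts by arm, day and cell type; Table 127 gives the between-arm counts.

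- **The test.** In SAP 9.2.1 "the statistical significance of the post- vs. pre-vaccination effect will be evaluated using a likelihood ratio testing the following hypothesis", and the null hypothesis is that post minus pre equals zero on the log2 scale. SAP 9.2.3 tests a zero difference between arms in the same way.
- **The rule.** Protocol 11.5.1.1: "Genes with a FDR-value < 0.05 and a fold change of greater or equal to 1.5-fold (up or down regulation) will be deemed" significantly DE. SAP 9.2 repeats it as "genes with an absolute fold change (effect size) of ≥ 1.5 compared to pre-vaccination or between Study Arms and FDR-adjusted p-value < 0.05", which attaches the label of effect size to the observed fold change. SAP 9.2 then allows the 1.5 cut-off to be changed according to the size of the effects observed.
- **The claim.** Protocol 11.5.1.1 refers to the "Benjamini-Hochberg procedure which controls the false positive rate among significantly differentially expressed genes". SAP 6.8 says that the BH false-discovery rates "will be used to control the false positive rate among significantly differentially expressed genes, proteins, and enriched pathways".

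Neither document plans a test against a minimum fold change or a confidence bound on the fold change.

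**The concern.** BH bounds the expected false share of the complete set it rejects. Here a further cut, on the observed fold change, is made within that set, and the term significantly DE is kept for what remains. The error statement is thus attached to a list for which BH provides no bound. The cut is also not neutral: in precise genes it removes almost everything, including true small changes, while in noisy genes it removes little, because a noisy gene that reaches significance already shows a large observed change.

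The count is a primary endpoint, and the DE genes feed the heatmaps, clusters, pathway enrichment and networks of SAP 9.3. A reader of the study report would take the list to be at most 5% false, and could take each gene on it to have changed at least 1.5-fold. Neither follows from the rule.

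**Working it through.** **Inputs from the documents.** 10 paired subjects per A/H7N9 arm (Protocol 5.2.4); 10,000 to 14,000 genes retained (SAP 9.1.6), 12,000 used here; BH at 0.05; fold cut log2(1.5) = 0.585.

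**Assumed, because the documents give no values.** The between-subject SD of the paired log2 fold change, the share of genes truly changed, and the sizes of the changes. The main check used a normal model with exact p-values in place of the negative binomial likelihood ratio test: estimate ~ Normal(true change, SD/√10), 200 runs per scenario. SD had median 0.2 to 0.6 and varied across genes in all but the first row below.

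**Step 1: the plan's own figure.** With 10% of genes truly changed, BH alone should give a false share of 0.05 × 0.90 = 4.5%. The simulation gave 4.5%, so the stated bound is reproduced for the BH list.

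**Step 2: what the fold cut does.** Take 500 BH rejections among 12,000 genes. The p-value threshold is 0.05 × 500/12,000 = 0.0021, or |z| ≥ 3.08. The fold cut demands |z| ≥ 0.585/(SD/√10):

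- SD 0.3: 0.585/0.0949 = 6.2, far stricter than BH.
- SD 0.8: 0.585/0.253 = 2.3, so the cut removes nothing that BH kept.
- The two thresholds meet at SD = 0.585 × √10/3.08 = 0.60.

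**Step 3: the false share after both rules.** Let F be the false share of the BH list, *a* the fraction of its false genes that survive the cut and *b* the fraction of its true genes that survive. Then

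false share = F·*a* / [F·*a* + (1 − F)·*b*],

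which rises if *a* > *b* and falls if *a* < *b*. Two scenarios with 10% of genes truly changed show both directions:

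- True changes of 1 plus an exponential with mean 0.3. BH list 473 genes, about 473 × 0.045 = 21 false. After the cut 225, about 225 × 0.027 = 6 false. So *a* ≈ 6/21 = 0.29 and *b* ≈ 219/452 = 0.48. The share falls to 2.7%.
- All true changes between 1.1- and 1.4-fold. BH list 500 genes, about 22.5 false. After the cut 54.6, about 54.6 × 0.128 = 7.0 false. So *a* ≈ 7.0/22.5 = 0.31 and *b* ≈ 47.6/477 = 0.10. The share rises to 12.8% (12.0% with 10,000 genes, 11.2% with 14,000).

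| True changes (10% of genes unless stated) | False share after both rules | Share of list truly below 1.5-fold, nulls included |
|---|---|---|
| All 2-fold, equal SD | 1.9% | 1.9% |
| 1.5 to 3 | 1.2% | 1.2% |
| 1.1 to 2 | 1.8% | 11% |
| 1 + exponential (mean 0.3), SD median 0.4 | 2.7% | 21% |
| Same, 2% of genes | 3.8% | 19% |
| Same, SD median 0.6 | 4.4% | 24% |
| Same, SD median 0.2 | 0.0% | 10% |
| 1 + exponential (mean 0.2), 30% of genes | 2.9% | 34% |
| All exactly 1.4 | 4.9% | 100% |
| 1.1 to 1.4 | 12.8% | 100% |

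**Step 4: weak effects concentrated in precise genes.** In the table, effect size is unrelated to a gene's SD. An edgeR simulation (quasi-likelihood F-test, 12 runs per scenario) instead put small shifts (SD 0.20 to 0.25 log2) in 30 to 40% of genes, all in the better-expressed half, with only 0.1 to 0.3% of genes changed 2-fold. BH only against both rules, mean list size and false share:

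- 311 (2.7%) against 71 (6.4%)
- 287 (3.3%) against 59 (10.1%)
- 631 (3.1%) against 144 (7.3%)
- 461 (2.6%) against 83 (9.7%)

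Genes truly at 1.5-fold or more in the filtered lists numbered 29 of 71, 15 of 59, 60 of 144 and 24 of 83, so roughly 58 to 75% of each list was below 1.5-fold. Normal-model runs of the same pattern gave 8 to 16% false. With small shifts absent or unrelated to precision, the share was 2 to 4%.

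**Step 5: observed against true fold change.** A gene with true change 1.4 shows an observed change of at least 1.5 with probability P(Z ≥ (0.585 − 0.485)/(SD/√10)): 0.15 at SD 0.3, 0.30 at 0.6 and 0.35 at 0.8.

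**The case against.** The study is declared exploratory (Protocol 11.2), and filtering on both significance and magnitude is a reasonable way to shorten a gene list. The clause in Protocol 11.5.1.1 describes the BH procedure before the double rule is given. SAP 9.2 provides for listings with estimates, raw and adjusted p-values, and for MA and volcano plots of all tested genes, so a careful reader can see both filters at work. All of this stands, and it limits the weight of the point. It does not rescue the error statement: SAP 6.8 attaches control to the significantly DE genes, and SAP 9.2 defines those by both rules.

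Three stronger readings are tempting, and the documents support none of them.

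- **That the list is more than 5% false.** Nine of the ten scenarios in the table stayed at or below 5%, mostly below BH alone. The excess needs weak effects to dominate with large ones rare or absent, and nothing in the documents says that this is the pattern. The edgeR runs also used a different test from the planned likelihood ratio test.
- **That the plan promises a true 1.5-fold change.** It only labels the observed change an effect size.
- **That the error differs between the AS03 and unadjuvanted arms.** No such difference has been shown, and SAP 9.2.3 compares the arms by a direct contrast, not by comparing two counts.

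**Conclusion.** The point holds as a matter of what is guaranteed. BH control applies to the list rejected at FDR < 0.05 against zero change. It does not extend to the subset that also passes an observed 1.5-fold cut, still less to one whose cut-off may move after the effects are seen. The size and direction of the departure are unknown: 0 to 5% false in most simulated scenarios, about 6 to 16% in the unfavourable ones. Every one of these figures rests on assumed variances and effect patterns. Separately, passing the cut does not establish a true change of 1.5-fold: with mixed effects, 10 to 34% of the filtered list fell short, and more where weak effects dominated. This is a stated property of a primary endpoint that should be corrected; it does not invalidate the analysis.

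**What to change.** 1. In Protocol 11.5.1.1 and SAP 6.8 and 9.2 (with the repeats in 9.2.1 and 9.2.3), say that the FDR < 0.05 statement applies to the BH-rejected list only.
2. In Tables 126 and 127, report the BH-only count beside the count that also passes the 1.5-fold cut. Label the second a descriptive filter on the estimate, with no guarantee on FDR or on effect size.
3. Fix the 1.5 cut-off before the data are seen. Report any revised cut-off as an additional result, not as a replacement.

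The cost is one extra column, and a less favourable error statement for the filtered list. The double rule itself can stay.

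Optional, and only if a claim about fold size is wanted: put the threshold inside the test (for example edgeR glmTreat) and apply BH to those p-values. The price is shorter lists. In the normal model a test against 1.5-fold cut one list from 225 genes to 52. In the edgeR runs glmTreat at 1.2-fold found 21, 8, 48 and 14 of the truly 1.5-fold genes, where the double rule found 29, 15, 60 and 24. A 1.2-fold null would also not support a 1.5-fold claim.
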